6.4 Administration Rate

Prior clinical trials have used rates up to 30×10^6 hMSC/min where no infusion related toxicity was observed.

In the proposed study, the cell dose to be delivered is 20 or 100 million cells in 80 mL Cells will be delivered at a rate of 2mL/min, and delivered at a maximum rate of 2.5×10^6 hMSC/minute and will last approximately 40 minutes for both doses.

The infusion bag will be flushed with an additional 25 ml of 0.9% normal saline at the completion of allo-hMSC infusion and delivered at a rate of 2ml/min.

6.5 Concomitant Therapy

6.5.1 Permitted therapy

Concomitant medications will be recorded on the case report form (CRF), which includes all FDA-approved medications, therapies, and dietary supplements.

6.5.2 Excluded therapy

Medications and therapies not approved by the FDA are prohibited for the duration of this trial, including participation with any investigational drug or device.

6.5.3. Subject monitoring

All aspects of the study will be conducted in accordance with Good Clinical Practice (GCP) as described in the ICH Guideline (CFR ICH Selected Regulations and Guidance for Drug

Studies, CFR Title 21 Food and Drugs Revised as of April 1, 2016) all applicable national and local regulations. Monitoring will be conducted by a qualified outside source at the study site.

Monitoring of key safety endpoints (refer to Table 8 in section 2.2.1) will be conducted.

6.6 Blinding and Un-blinding

Subjects will be randomized into active groups. Only designated technicians in the ISCI Cell Processing Laboratory will be unblinded to treatment. The investigator, study staff, subject and anyone involved in the care of the subject will not be made aware of the assigned treatment regimen. Before dispensing the investigational product, Cell Therapy Lab staff will confirm the CMV status of eligible recipient. This information will be used to select Allo-BM and UC MSC product. CMV status of the recipient and donor of the Allo-BM and UC MSC product will be matched. CMV positive Allo-BM or UC MSC product will only be infused to a CMV positive recipient. All CMV negative recipients will receive CMV negative Allo-BM or UC MSC product¹³⁴.

The designated cell-processing technicians will prepare both (BM and UC) the allogeneic MSCs infusions. The investigational agent infusions will be prepared in identical infusion bags and labeled with the identical investigational drug labels. A brown plastic slip cover will be placed over the infusion lines as well as the bags to maintain the blind. The designated technicians in the ISCI Cell Processing Laboratory (or designee) will be responsible for maintaining the investigational product records including randomized treatment assignments by subject identification.

If for important medical reasons un-blinding is thought to be necessary, the Investigator may identify the treatment assignment by obtaining the randomization assignment by contacting the Director of Experimental and Clinical Cell Based Therapies at ISCI who is responsible for maintaining randomization records for all subjects.

6.7 Study Investigational Therapy Management

6.7.1 Investigational Product Labeling and Storage

The product label contains the elements required by the CFR and other national and local authorities for investigational products. ISCI CMP will directly store and deliver the designated cell processing technologist in the CPL, and will be kept cryopreserved in a liquid nitrogen vapor phase until shortly before administration and must be stored in a securely locked enclosure. Access is strictly limited to unblinded CPL personnel prior to preparation for infusion. After preparation for infusion, the Investigator and his or her designees are permitted to administer the Investigational Product only to subjects participating in this protocol.

6.7.2 Investigational Product Accountability Procedures

In accordance with all applicable regulatory requirements, the Cell Processing Laboratory will maintain a record of the investigational products BMMSCs or UCMSCs received, dispensed, administered, destroyed, or returned. The final disposition of all unused, empty, and partially used Cryocyte™ bags will be handled in accordance with the drug preparation manual.

Only unblinded personnel may access accountability records until the study blind has been broken.

7. STUDY PROCEDURES

7.1. Time and Events Schedule

The Time and Events Schedule for the conduct of this study is shown in **Table 11**

Schedule of Assessments
Table 11: Time and Events Table

VISIT	Screening + 45 days	Baseline (0 to -4 weeks prior to Day 0)	Day 0	Week 2 (Day 14) ± 2 days	Month 1 (Day 30) ±1 weeks	Month 3 (Day 90) ±4 weeks	Month 6 (Day 180) ±6 weeks	Month 12 (Day 365) ±2 weeks
Informed Consent	X							
Full Medical History	X							
Physical Exam	X	X	X	X	X	X	X	X
Vital Signs ¹	X	X	X	X	X	X	X	X
12-lead (ECG)	X	X	X	X	X	X	X	X
Concomitant Medications	X	X	X	X	X	X	X	X
Randomization		X						
Infusion Treatment (IP)			X					
6 Minute Walk Test			X			X	X	
4 Meter Gait Speed Test			X			X	X	
QOL Questionnaires (EQ-5D, SF-36, IIEF (Male), SQOL-F(Female))		X			X	X	X	
Laboratory Testing ²								
Review Adverse Events		X	X	X	X	X	X	X
Brachial Ultrasound ³	X	X				X		
Dobutamine Stress Echo (DSE) ⁴	X						X	

Subjects in the pilot phase will receive a telephone call 5 days post infusion (+/- 1 day) to review adverse events

- 1- Weight, Height (will only be collected at screening)
- 2- See table 12 for specific tests done at each time point
- 3- Brachial ultrasound to assess endothelial function should be completed in the morning prior to 12p.m. Instruction for completing this assessment are outline in Appendix 3 of this protocol
- 4- Dobutamine Stress Echocardiogram (DSE) will be performed, at screening and at the Month 6 follow-up visit. Instructions for completing the (DSE) are outlined in Appendix 2 of this protocol. If the stress test needs to be stopped due to unforeseeable side effects and cannot be completed on a subject, this will not prevent them from being able to take part in the study.

Schedule of Laboratory Testing
Table 12: Time and Events Table

VISIT		SCR	BSL	DAY 0	W2	M 1	M 3	M 6	M 12
Standard Labs	CBC with Differential ¹	X		X	X	X	X	X	
	Comprehensive Metabolic Panel ²	X		X	X	X	X	X	
	PT, INR, PTT	X							
	Uric Acid, Pro BNP, hsCRP, IL6, Fib, D-dimer, TNFa,	X		X	X	X	X	X	
	Lipid Profile ³	X		X	X	X	X	X	
	Urinalysis	X		X		X	X	X	
	HbA1c	X				X	X	X	
	Pregnancy (childbearing women) ⁴	X		X					
Biomarkers / Immune	SST / PRA ⁵			X				X	
	MNCs ⁶			X	X	X	X	X	
EPCs	Endothelial Blood Samples ⁷		X				X		
Gene Expression	DNA ⁸			X					
	RNA			X				X	
Viral Serology	Infectious Disease Tests ⁹	X							

1. Complete Blood Count with Differential - WBC, RBC, hemoglobin, hematocrit, MCV, and platelets; Diff: neutrophils, lymphocytes, monocytes, eosinophils, and basophils.
2. Complete Metabolic Panel – glucose, sodium, potassium, chloride, bicarbonate, blood urea nitrogen, creatinine, total protein, albumin, alkaline phosphatase, total bilirubin (fractionate if total >1.5 times normal), alanine transaminase (ALT), aspartate transaminase (AST), and GFR.
3. Lipid Profile: Triglyceride levels, Total cholesterol, LDL levels, and HDL levels
4. Pregnancy Serum β HCG: will be completed within 36 hours prior to infusion
5. SST: (2 Gold or Tiger top tube) Transcriptomic/proteome (RNA, mRNA, protein samples, and telomerase, akt); growth factors (sdf-1, notch); functional assays (cell-growth rate, VEGF, and CFU assays) and more.
6. MNCs: (2 Green top tube) CD3*CD25* or CD3*CD69* and more
7. Endothelial Blood Samples: (5 Lavender top tubes) Endothelial Progenitor Cell- Colony Forming Units (EPC-CFU). Must be performed on the same day as the day as the brachial artery ultrasound.
8. Genetic Testing: Deoxyribonucleic acid (DNA) to be collected at one time point only.
9. Infectious disease tests – HIV, HIV 2, Hep B (HBsAg, HBs Ab, HBc Ab), Hep C (Anti-HCV), VDRL/Syphilis (reflex FTA Ab), and CMV.

7.1.1 Remote Visits

Since trial participants may not be able to come to the investigational site for protocol specified visits during the “Coronavirus disease 2019” (Covid-19) pandemic, alternative methods for assessments (e.g., phone contact, virtual visit, alternative location for assessment, including local labs or imaging centers) could be implemented when necessary and feasible, and would be sufficient to assure the safety of trial participants. Assessments can be completed as follows:

- Physical Examination – Can be completed via telemedicine using a virtual platform.
- Vital Signs and 12-lead EKG – If subject has completed an EKG or vital signs within the protocol specified time window with their PCP or any other treating physician, a copy can be requested. Alternatively, subjects may record and report their own vital signs or EKG using home testing equipment (such as thermometer, automated blood pressure monitor, pulse oximeter, wearable health devices, or other method for recording vital signs).
- Questionnaires, concomitant medications and review of adverse events – may be completed by study team via email, phone contact, virtual visit or alternative methods.
- Laboratory assessments – A copy of SOC labs (urinalysis, hematology, chemistry, Hg A1C , lipid profile as well as any labs required by the protocol for particular time point) may be obtained from PCP or treating physician if done within the protocol specified time window. If participant has not completed any laboratory assessment they may complete them in any local laboratory facility.
- Brachial Artery Ultrasound, 6 minute walk test, 4 meter gait speed test, Dobutamine Stress Echo, Immune Monitoring, EPC-CFUs and Biomarkers Assessment – if participant is willing to come to site to complete these assessments, all necessary safety precautions will be taken. Study team will provide the subject with a mask and gloves upon arrival to the site. If subject prefers to complete this assessment at another time, the study team must document if the assessment will be completed out of the protocol specified time window and report to the regulatory authorities accordingly.

7.2 Study Phases and Visits

7.2.1 Screening Visit

See Table 11 for the procedures and assessment to be performed during the screening visit of the study. All screening visit test and procedures will occur upon signing the informed consent form (ICF). No screening exams will take place until the subject is fully informed of the research and signs the consent form. The tests may take place over several days and will need to be completed prior to performing the baseline visit. There will be up to a 45-day window from the time the subject signs the informed consent form to the baseline visit to complete screening procedures.

A subject may be rescreened based on the Investigators judgement and will at a minimum need to reconsent and complete screening laboratory tests. The subject will remain with the same subject number throughout this process.

7.2.2 Baseline Visit

See Table 1 for the procedures and assessment to be performed during the baseline visit of the study. This visit will occur after all screening tests are completed and it has been determined that the subject meets eligibility criteria. This visit should occur within 4 weeks prior to Day 0 (the infusion visit).

7.2.3 Day 0 Visit

See Table 11 for the procedures and assessment to be performed during the Day 0 visit of the study. The Day 0 visit will occur after all baseline tests are completed and it has been determined that the subject remains eligible. Once the subject is deemed eligible to continue in the study the subject will be administered the investigational product.

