4.2 Exclusion Criteria

In order to participate in this study, a subject MUST NOT:

1. Be a female who is pregnant, nursing, or of childbearing potential while not practicing effective contraceptive methods. Female subjects must undergo a blood or urine pregnancy test at screening and within 36 hours prior to infusion.
2. Inability to perform any of the assessments required for endpoint analysis.
3. Active listing (or expected future listing) for transplant of any organ.
4. Clinically important abnormal screening laboratory values, including but not limited to: hemoglobin <8 g/dl, white blood cell count <3000/mm³, platelets <80,000/mm³, INR > 1.5 not due to a reversible cause (i.e. Coumadin), aspartate transaminase, alanine transaminase, or alkaline phosphatase > 3 times upper limit of normal.
5. Serious comorbid illness that, in the opinion of the investigator, may compromise the safety or compliance of the subject or preclude successful completion of the study. Including, but not limited to: HIV, advanced liver or renal failure, class III/IV congestive heart failure, myocardial infarction, unstable angina, or cardiac revascularization within the last six months, or severe obstructive ventilatory defect.
6. Have known allergies to penicillin or streptomycin.
7. Be a solid organ transplant recipient. This does not include prior cell-based therapy (>12 months prior enrollment) bone, skin, ligament, tendon or corneal grafting. Have a history of organ or cell transplant rejection.
8. Have a clinical history of malignancy within 3 years (i.e., subjects with prior malignancy must be disease free for 3 years), except curatively-treated basal cell carcinoma, squamous cell carcinoma, melanoma in situ or cervical carcinoma, if recurrence occurs.
9. Have a non-pulmonary condition that limits lifespan to < 1 year.
10. History of drug abuse (illegal "street" drugs except marijuana, or prescription medications not being used appropriately for a pre-existing medical condition) or alcohol abuse (\geq 5 drinks/day for > 3 months), or documented medical, occupational, or legal problems arising from the use of alcohol or drugs within the past 24 months
11. Be serum positive for HIV, hepatitis BsAg or Viremic hepatitis C, and/or Syphilis – VDRL (If VDRL is reactive Confirmation with FTA-ABS is needed (Syphilis)).
12. Be currently participating (or participated within the previous 30 days) in an investigational therapeutic or device trial.

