9. STATISTICAL ANALYSIS

9.1 Determination of Sample Size and Analysis Population

No formal statistical justification was performed to determine sample size in the Phase I study. Cohort size was determined based on expected requirements for safety analyses and projected enrollment rates. Study participants will be randomized according to a fixed allocation permuted block randomization schema. The allocation ratio will be 1:1:1:1 and the block size will be 4. All enrolled subject who received at least one treatment dose will be included in summaries of baseline characteristics, safety, and efficacy. Reasons for study discontinuation will be tabulated.

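### Randomisation is scheduled at Baseline, up to 4 weeks before infusion and ahead of the last eligibility check, so arms of 10 can end short or unbalanced

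*Combined protocol and SAP*

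**What the plan says.** **Timing of allocation.** Table 11 (section 7.1) marks randomisation in the column headed "Baseline (0 to -4 weeks prior to Day 0" and marks the infusion in the Day 0 column. Section 7.2.2 agrees on the window: "This visit should occur within 4 weeks prior to Day 0 (the infusion visit".

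**First eligibility decision.** Section 7.2.2 places it before the Baseline visit, which follows once "it has been determined that the subject meets eligibility criteria".

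**Second eligibility decision.** Section 7.2.3 reads: "The Day 0 visit will occur after all baseline tests are completed and it has been determined that the subject remains eligible". Infusion depends on it: "Once the subject is deemed eligible to continue in the study the subject will be administered the investigational product". Exclusion criterion 1 in section 4.2 also requires a repeat pregnancy test "within 36 hours prior to infusion", and Table 12 lists that test under Day 0.

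**Analysis population.** Section 9.1: "All enrolled subject who received at least one treatment dose will be included" in the summaries of baseline characteristics, safety and efficacy. The same section says that reasons for discontinuation will be tabulated. No set of all randomised subjects is defined.

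**Replacement.** Section 4.4 allows, where judged necessary, replacement of subjects who withdraw for reasons unrelated to the study or its product, under new identification numbers. It does not mention a failed eligibility re-check or the arm that the replacement joins.

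**Size.** The synopsis plans 10 treated subjects in each of three randomised groups, 30 in all. Section 9.1 reports no formal sample-size justification and states no allowance for loss.

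**The concern.** Allocation normally comes after the last point at which a subject can be turned away. Here the schedule allows the reverse order, with up to 28 days between the two. The re-check is a real one:

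- The pre-infusion pregnancy test falls after allocation unless Baseline is itself within 36 hours of infusion.
- Brachial ultrasound is repeated at Baseline, and FMD below 7% is inclusion criterion 3. The plan does not say whether a Baseline reading at or above 7% ends eligibility, or whether the scan precedes allocation on that day.
- An exclusion 5 event, such as an infarction or unstable angina, or a withdrawal of consent can occur during the gap.

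Such a subject has used an allocation but contributes nothing to the dosed summaries. In arms of 10, each one is 10% of the arm. If the plan does not say how the place is refilled, the intended 10/10/10 is left to chance and discretion, in a trial whose primary comparison already rests on very small groups.

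**Working it through.** The plan offers no power calculation to reproduce. Its count is consistent: 4 pilot groups of 3 plus 3 randomised groups of 10 is 12 + 30 = 42.

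**Inputs from the documents:** 30 randomised subjects, 10 per arm (synopsis); maximum gap 4 weeks, 28 days (Table 11, section 7.2.2); primary endpoint TE-SAE incidence within one month of infusion (section 2.2.1); two-sided 95% intervals (section 9.2).

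**Input not in the documents:** the proportion q of randomised subjects who are never infused. I assume 3%, 5% and 10%, independent between subjects, and count losses before any replacement.

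**Step 1. How likely is at least one loss?** Expected losses are 30q; the chance of at least one is 1 − (1 − q)^30.

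| q | Expected losses | Chance of at least one |
|---|---|---|
| 3% | 0.9 | 1 − 0.97^30 = 60% |
| 5% | 1.5 | 1 − 0.95^30 = 79% |
| 10% | 3.0 | 1 − 0.90^30 = 96% |

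**Step 2. How likely is an arm of 8 or fewer?** For one arm, the chance of two or more losses is t = 1 − (1 − q)^10 − 10q(1 − q)^9; for any of three arms it is 1 − (1 − t)^3. This gives 24% at q = 5% and 60% at q = 10%.

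**Step 3. What does a short arm cost?** With no TE-SAEs in an arm of n, the exact two-sided 95% upper limit is 1 − 0.025^(1/n). For a mean comparison of two arms of n at two-sided 0.05 and 80% power (normal approximation), the detectable difference is (1.96 + 0.84) × √(2/n) SD.

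| n | Upper limit, no events | Detectable difference |
|---|---|---|
| 10 | 30.8% | 1.25 SD |
| 9 | 33.6% | 1.32 SD |
| 8 | 36.9% | 1.40 SD |

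**Step 4. Does the replacement rule restore 10 per arm?** Set against the two routes to loss:

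- *Withdrawal of consent in the gap.* Section 4.4 names this as an example, so replacement is allowed but not required.
- *Failed re-check.* Section 4.4 speaks of subjects who withdraw, and its examples are withdrawn consent and loss to follow-up. A subject found ineligible is not clearly included.
- *Arm of the replacement.* Not stated. Under a permuted-block list, a subject with a new number would ordinarily take the next code, which need not be the vacated arm.
- *Rescreening.* Section 7.2.1 lets a rescreened subject keep the same number, without saying whether an earlier allocation stands.

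Replacement can therefore restore the total of 30 without restoring 10 in each arm.

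**The case against.** Several points on the other side are sound.

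- **Endpoint and blinding.** The primary endpoint is counted from infusion, so a dosed population suits it. Section 6.6 blinds the investigator, study staff and subject, so a pre-infusion exclusion should not depend on the arm. Efficacy is exploratory, and there is no power claim to undermine. A reader might infer that the comparison is biased; the documents show no mechanism that would do it.
- **Replacement and reporting exist.** A reader might infer that these subjects vanish and cannot be replaced. That goes too far: section 4.4 permits some replacement, section 9.1 tabulates reasons for discontinuation, and the DSMB reports in section 9.4.3.3 cover enrolment, discontinuations and withdrawals. The synopsis target also counts treated subjects.
- **Timing.** A reader might infer that eligibility is re-decided only on Day 0, always weeks after allocation. Section 7.2.3 makes the finding a condition for the Day 0 visit, so it lies between Baseline and Day 0 or on Day 0. The window starts at 0, so both visits may fall on one day, and 28 days is the maximum.
- **Lead time.** A reader might infer that early allocation has no use. Section 6.7.1, on cryopreserved storage, does not say that. The laboratory must select CMV-compatible product (section 6.6), and placebo needs quality-control testing before use (section 5.1).

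What remains is that the schedule permits allocation before the last check, and that the replacement rule neither clearly covers a failed re-check nor fixes the arm.

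**Conclusion.** The point holds as a weakness in sequence and specification. The order of allocation and final eligibility check exposes arms of 10 to avoidable loss and imbalance, and section 4.4 only partly guards against it.

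The size is moderate and conditional. The 60% to 96% chance of at least one uninfused subject rests on assumed rates of 3% to 10% and ignores replacement. The cost per affected arm needs no such assumption: with no events, the upper limit moves by 2.8 percentage points for one lost subject (33.6 − 30.8) and 6.1 for two (36.9 − 30.8). Given the blinding and the post-infusion endpoint, the main harm is to precision and balance, not demonstrated bias.

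The 1:1:1:1 ratio with blocks of 4 in section 9.1, against three arms and the 1:1:1 of section 9.3, is a separate inconsistency that needs its own correction.

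**What to change.** In Table 11, move randomisation from Baseline to Day 0, or to the 36 hours before infusion. Permit it only when the baseline tests and the pre-infusion pregnancy test have been reviewed, continued eligibility has been confirmed in writing, and the recipient's CMV status is available; CMV is already tested at screening (Table 12). In sections 7.2.2 and 7.2.3, state that a subject who fails the re-check is a screen failure and uses no randomisation number.

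If the current order is kept, section 9.1 should require randomised but uninfused subjects to be reported by arm with reasons, and section 4.4 should say whether a failed re-check qualifies for replacement and which arm the replacement takes.

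The cost is an amendment to one table and a few sentences. The practical downside is shorter notice for the cell laboratory, which must have CMV-suitable product of each cell type, and placebo, available for each infusion slot. Cryopreserved storage until shortly before administration (section 6.7.1) keeps that burden small.

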7.2.4 Week 2 Visit

See Table 11 for the procedures and assessment to be performed for the week 2 visit of the study. Outpatient visits should be completed as close to the scheduled visit dates as possible. There will be a window of +/- 2 days for the week 2 study visits.

